---	-------------------------------------	--------

2 LIST OF ABBREVIATIONS

Abbreviation	Definition
AE	adverse event
ALT	alanine transaminase
AST	aspartate aminotransferase
ATC	Anatomical Therapeutic Chemical
BMI	body mass index
BUN	blood urea nitrogen
CDF	cumulative distribution function
CSR	Clinical Study Report
CTCAE	Common Terminology Criteria for Adverse Events
DMC	Data Monitoring Committee
ECG	electrocardiogram
HAE	hypersensitivity adverse event
Hg	mercury
IgE	immunoglobulin E
IgG	immunoglobulin G
IgM	immunoglobulin M
LOCF	last observation carried forward
MedDRA	Medical Dictionary for Regulatory Activities
Nab	neutralizing antibody
NCI	National Cancer Institute
NIAID/FAAN	National Institute of Allergy and Infectious Disease/Food Allergy and Anaphylaxis Network
PAL	phenylalanine
PEG	polyethylene glycol
Phe	phenylalanine
PK	pharmacokinetics
PKU	phenylketonuria
PT	preferred term
rAvPAL-PEG	recombinant Anabaena variabilis phenylalanine ammonia lyase-PEG
SAP	Statistical Analysis Plan
SOC	system organ class
SMQ	Standardized MedDRA Queries
TEAE	treatment-emergent adverse event
Tab	total antibody
ULN	upper limit of normal
WHODrug	World Health Organization Drug Dictionary

	SAP PAL-003 Amendment 1 version 1.0	Page 6
---	-------------------------------------	--------

3 INTRODUCTION

This Statistical Analysis Plan (SAP) describes the statistical analysis methods and data presentations to be included in the Clinical Study Report (CSR) for PAL-003, Long-term Extension of a Phase 2, Open-Label, Dose-Finding Study to Evaluate the Safety, Efficacy, and Tolerability of Multiple Subcutaneous Doses of rAvPAL-PEG in Subjects with PKU. This SAP includes the data summary methodologies for analysis of safety, efficacy, and pharmacokinetics (PK) data. Results obtained from the analyses described in this document will provide the basis of the CSR for this study. Analysis methods specified in this document take precedence over those described in the protocol should there be any differences.

3.1 Objectives of Study

The primary objective of the study is:

- To evaluate the effect of long-term administration of multiple doses of subcutaneous (SC) injections of pegvaliase (also described as rAvPAL-PEG or pegvaliase) on blood Phe concentrations in subjects with phenylketonuria (PKU).

The secondary objectives of the study are:

- To evaluate the safety and tolerability of long-term administration of SC injections of pegvaliase in subjects with PKU.
- To evaluate the immune response to long-term administration of SC injections of pegvaliase in subjects with PKU.

The exploratory objectives of the study are:

- To evaluate the long-term relationship of diet and change in blood Phe concentration following administration with pegvaliase in subjects with PKU.

The Substudy objectives are as follows:

- To evaluate steady-state PK of pegvaliase in subjects who have achieved and maintained target blood Phe concentration and for whom no further dose modifications are planned.

3.2 Study Design

This is a long-term extension of pegvaliase Phase 2 studies in subjects with PKU. The doses are planned to be in the same range as those tested in phase 2 (starting at 0.001 through 5.0 mg/kg/week or 2.5 mg through 375 mg/week), provided no dose-limiting toxicity is observed in a previous pegvaliase study.

Only subjects who completed a previous pegvaliase study will be enrolled into this study. Subjects enrolling into PAL-003 with no interruption in dosing from a previous pegvaliase

Proprietary and Confidential

	SAP PAL-003 Amendment 1 version 1.0	Page 7
---	-------------------------------------	--------

study may either continue their previous dosing regimen or begin this study at a higher dose level. Subjects who have had dosing interruptions between the previous pegvaliase study and PAL-003 must have their starting dose determined per the Sponsor's Medical Officer.

A PK substudy has been added to evaluate the steady-state PK of pegvaliase in up to 6 subjects who have achieved and maintained target blood Phe for at least 2 consecutive measurements and for whom no further dose modifications are planned. Subjects enrolled into the substudy will have additional pre-dose PK sampling performed.

3.3 Study Population

Only subjects who completed a previous pegvaliase study will be enrolled into this study.

3.4 Study Dosage and Administration

Pegvaliase will be provided in vials or prefilled syringes; subjects will be supplied with vials and syringes or prefilled syringes for administration in the clinic and self administration:

- Pegvaliase will be provided in 3 mL (milliliter) vials, each containing 1.5 ± 0.2 mL to deliver 15 mg of rAvPAL-PE per 1.0 mL (15 mg/mL protein concentration). Each vial is filled with 1.5 ± 0.2 mL to allow the withdrawal and delivery of up to 1.0 mL of the drug product.
- Or
- Pegvaliase will be provided in 3-mL vials, each containing 1.8 ± 0.3 mL to deliver 20 mg of rAvPAL-PE per 1.3 mL (15 mg/mL protein concentration). Each vial is filled with 1.8 ± 0.3 mL to allow withdrawal and delivery of up to 1.3 mL.
- Or
- Pegvaliase will be provided in prefilled syringes in three sizes that deliver up to 1 mL. Syringe sizes are 2.5 mg (5 mg/mL protein concentration), 10 mg (20 mg/mL protein concentration), and 20 mg (20 mg/mL protein concentration).

Pegvaliase may be administered SC from 0.001 to a maximum weekly dose of 5.0 mg/kg or 375 mg/week.

3.5 Sample Size Determination

Subject who participated in a previous pegvaliase study may be enrolled into this study. No formal sample size calculation was conducted.

3.6 Blinding and Randomization Methods

This is an open-label study.

	SAP PAL-003 Amendment 1 version 1.0	Page 8
---	-------------------------------------	--------

3.7 Interim Analysis

There is no formal interim analysis planned.

	SAP PAL-003 Amendment 1 version 1.0	Page 9
---	-------------------------------------	--------

4 GENERAL ANALYSIS CONSIDERATION

Descriptive summaries of continuous variables will include the number of subjects (n), mean, standard deviation, median, minimum, and maximum. Descriptive summaries of categorical variables will include n and percent. Data from parent studies (PAL-002, PAL-004, 165-205) will be integrated together with data in PAL-003 for long term safety and efficacy analysis. The baseline value of an assessment is defined as the last available measurement prior to first administration of study drug from parent studies (PAL-002, PAL-004, 165-205), unless otherwise specified.

4.1 Analysis Populations

4.1.1 Efficacy

The efficacy population will consist of all subjects who receive at least one dose of study drug and have post-treatment blood Phe concentration measurements in any of the phase 2 studies (PAL-002, PAL-004, 165-205, PAL-003).

4.1.2 Safety

The safety population will consist of all subjects who receive at least one dose of study drug throughout the study duration of any of the phase 2 studies (PAL-002, PAL-004, 165-205, PAL-003).

4.1.3 PK

The PK population will consist of all subjects who receive any amount of study drug and have post-treatment plasma pegvaliase concentration measurements in any of the phase 2 studies (PAL-002, PAL-004, 165-205, PAL-003).

4.2 Treatment Group Presentation

Unless specified otherwise, analyses will be presented by parent Phase 2 studies (PAL-002, PAL-004, 165-205) combined, PAL-003, and all Phase 2 studies (PAL-002, PAL-004, 165-205, PAL-003) combined.

The following treatment groups may also be considered in the summary tables for corresponding assessments:

For [REDACTED], analyses will be presented by current [REDACTED]

[REDACTED] at each assessment visit in both parent studies (PAL-002, PAL-004, 165-205) and PAL-003. The weekly dose is defined as the [REDACTED] prior to each assessment.

	SAP PAL-003 Amendment 1 version 1.0	Page 10
---	-------------------------------------	---------

[REDACTED]), analyses will be presented by daily [REDACTED] on or prior to AE onset date in both parent studies (PAL-002, PAL-004, 165-205) and PAL-003.

4.3 Pooling of Data from Sites with Small Enrollment

Due to small sample sizes at each site, separate analyses by site or pooled site will not be performed.

4.4 Study Day Derivation

Unless otherwise specified, the first study drug administration date for pegvaliase from parent studies (PAL-002, PAL-004, 165-205) is considered study day 1 and is used as the reference date for the derivation of study day in data displays. Study day is computed by subtracting study day 1 from a visit date plus 1 if the visit date occurs on or after the initial study drug start date. Otherwise, the study day will be the visit date minus the study day 1. There is no Study Day 0.

4.5 Visit Window for Analysis

An assessment for a subject will be classified according to the study day of the assessment where it falls within a visit window. The windows are designated for each scheduled visit with a target day. If there are two or more assessments within a designated window, the assessment that is closest to the target day will be used for analyses. If the two closest assessments to the target day are equidistant from the target day, then the average of the two assessments will be used for analyses. If the measurement is a laboratory categorical variable, however, then the worse of the 2 equidistant measurements will be used.

Table 1 lists the visits assigned for the analyses of all assessments and the corresponding range of treatment days (window) during which a visit may have occurred by analysis parameter.

BIOMARIN®	SAP PAL-003 Amendment 1 version 1.0	Page 11
------------------	-------------------------------------	---------

Table 1: Visit Time Windows for the Treatment Period

Scheduled Time Point	Target Day	Visit Window
Baseline		Last measurement prior to pegvaliase administration from parent studies (PAL-002, PAL-004, 165-205)
Week 4	Day 22	Day 8 to Day 35
Week 8	Day 50	Day 36 to Day 63
Week 12	Day 78	Day 64 to Day 91
Week 16	Day 106	Day 92 to Day 119
Week 20	Day 134	Day 120 to Day 147
Week 24	Day 162	Day 148 to Day 175
...
Week 388	Day 2710	Day 2696 to Day 2723
Week 392	Day 2738	Day 2724 to Day 2751
Week 396	Day 2766	Day 2752 to Day 2779
Week 400	Day 2794	Day 2780 to Day 2807
Week 404	Day 2822	Day 2808 to Day 2835
Week 408	Day 2850	Day 2836 to Day 2863
Week 412	Day 2878	Day 2864 to Day 2891
Week 416	Day 2906	Day 2892 to Day 2919
Every 4 weeks		

Blood Phe concentration will also be summarized based on the data collected in PAL-003 and visits in [Table 2](#). For this analysis, the first study drug administration date for pegvaliase from PAL-003 is considered as study day 1 and is used as the reference date for the derivation of study day in data displays.

BIOMARIN®	SAP PAL-003 Amendment 1 version 1.0	Page 12
------------------	-------------------------------------	---------

Table 2: Visit Time Windows for the Treatment Period in PAL-003

Scheduled Time Point in PAL-003	Target Day in PAL-003	Visit Window in PAL-003
PAL-003 Baseline		Last measurement prior to pegvaliase administration from PAL-003
Week 4	Day 22	Day 8 to Day 35
Week 8	Day 50	Day 36 to Day 63
Week 12	Day 78	Day 64 to Day 91
Week 16	Day 106	Day 92 to Day 119
Week 20	Day 134	Day 120 to Day 147
Week 24	Day 162	Day 148 to Day 175
		Every 4 weeks

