14.1 Immunogenicity

Immunogenicity testing will be performed using validated immunogenicity assays. Blood samples for routine immunogenicity testing will be collected prior to dosing as indicated in the protocol. Routine immunogenicity testing will include assays for anti-rAvPAL immunoglobulin G (IgG), anti-rAvPAL IgM, anti-PEG IgM, anti-PEG IgG, and neutralizing antibodies (NAb). In the event of a Hypersensitivity Reaction visit, sampling and testing will be performed for anti-rAvPAL-PEG IgE and anti-rAvPAL IgE as well as other potentially-related clinical laboratory tests, including CRP, C3/C4, and tryptase.

For immunogenicity analysis, an incidence table will be provided for PAL IgG, PAL IgM, PEG IgG, PEG IgM, and NAb. Titer summary statistics will also be provided for PAL IgG and PEG IgG, including mean, median, standard deviation, and minimum/maximum titer values at each study visit. The mean titers for PAL IgG and PEG IgG and percent positivity for PAL IgM, PEG IgM and NAb will be plotted over time. A listing of anti-rAvPAL-PEG IgE and anti-rAvPAL IgE test results will be provided by subject.

Anti-drug antibody impact on long-term safety will be evaluated. Plots and tables will be generated to explore the potential impact of anti-drug antibodies on hypersensitivity adverse event (HAE) frequency and severity. A listing will be provided of all hypersensitivity reaction visits with the most proximal antibody test result listed for each analyte, and when available, CRP, complement C3 and C4, and tryptase at the time of the event.

Anti-drug antibody impact on long-term efficacy will be evaluated. Plots and tables will be generated to explore the potential impact of anti-drug antibodies on blood Phe levels

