14.2 Clinical Laboratory Tests

Standard descriptive statistics will be presented for clinical laboratory tests, including hematology, chemistry and urinalysis, at each scheduled visit and for change in laboratory values from baseline from parent studies (PAL-002, PAL-004, 165-205) to each scheduled visit. The proportion of subjects who experienced at least one laboratory test result with CTC grade as 3 or above and who experienced at least one laboratory test results outside the normal ranges will be presented for each measurement. Shift tables will be created for

	SAP PAL-003 Amendment 1 version 1.0	Page 27
---	-------------------------------------	---------

selected laboratory parameters in clinical chemistry, hematology, and urinalysis (white blood cells [WBCs], neutrophils, eosinophils, basophils, erythrocyte sedimentation rate [ESR], serum creatinine, serum blood urea nitrogen [BUN], C3, C4, C-reactive protein [CRP], urine microalbumin, urine albumin/creatinine ratio, aspartate transaminase [AST], alanine transaminase [ALT], and total bilirubin, creatinine phosphokinase [CPK], hemoglobin decrease) to summarize the change in laboratory value from baseline to worst post-baseline value based on normal range (low, normal, and high) or National Cancer Institute (NCI) Common Terminology Criteria for Adverse Events (CTCAE) grading, where available. Results of complement 3, complement 4, C-reactive protein, micro albumin, urine albumin/creatinine ratio, aspartate aminotransferase (AST), alanine aminotransferase (ALT), bilirubin, serum creatinine, creatinine, and blood urea nitrogen (BUN) will be plotted overtime. A subject listing of laboratory test results for hematology, chemistry, urinalysis, and other laboratory tests will be provided separately. Values with CTC grade as 3 or above will be flagged in the listings. A listing of laboratory test results for subjects with ALT or $AST \geq 3x$ the upper limit of normal (ULN) and total bilirubin $\geq 2xULN$ will also be provided.

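### The visit-window rule selects by study day only, so CRP and C3/C4 drawn because of a hypersensitivity reaction can displace or stand in for routine values in the by-visit displays

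*SAP*

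**What the plan says.** **Section 4.5** places assessments in windows by day: "An assessment for a subject will be classified according to the study day of the assessment where it falls within a visit window". The scope is general: "Table 1 lists the visits assigned for the analyses of all assessments". When a window holds several values, "the assessment that is closest to the target day will be used for analyses". If the two nearest are equidistant, "then the average of the two assessments will be used for analyses". For a categorical laboratory variable, "then the worse of the 2 equidistant measurements will be used". None of these steps refers to visit type or to the reason for the draw.

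**Section 14.1** adds event-driven sampling: "In the event of a Hypersensitivity Reaction visit, sampling and testing will be performed". Besides IgE, this covers "potentially-related clinical laboratory tests, including CRP, C3/C4, and tryptase". Reaction visits also get a listing of their own.

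**Section 14.2** gives descriptive statistics for laboratory tests at each scheduled visit, and names C3, C4 and CRP among its laboratory shift-table parameters. The over-time plots name them again: "Results of complement 3, complement 4, C-reactive protein, micro albumin". Tryptase is not among the plotted analytes.

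No section excludes reaction-visit samples from window selection or gives routine draws priority.

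**The concern.** CRP and complement are measured at a reaction visit because they may be abnormal at that moment. If such a sample is eligible for a visit window on the same terms as a routine one, the chance that a value is observed depends on the outcome being described. That is informative sampling, and it does not average out.

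At stake is the reading of inflammation and complement over years of dosing. Section 14 also plots the number of hypersensitivity AEs over time. A CRP or complement display that partly reflects when reactions happened could seem to corroborate that plot, when some of the agreement was built in by the selection rule.

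**Working it through.** **1. Reproduce the windows.** The printed rows of Table 1 follow target = 7 × (week − 1) + 1, with a window from target − 14 to target + 13.
- Week 4: 7 × 3 + 1 = Day 22, window Day 8 to 35.
- Week 416: 7 × 415 + 1 = Day 2906, window Day 2892 to 2919.

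All 14 printed rows match. The windows are 28 days wide and contiguous from Day 8, so on this pattern every on-treatment sample from Day 8 onward falls in some window.

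**2. When does a reaction sample enter?** Let the routine draw lie s days after target and the reaction sample fall on any of the 28 days with equal chance (an assumption). It replaces the routine value if it is fewer than s days from target, and is averaged with it at exactly s days.

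| Routine draw | Replaces | Replaces or is averaged |
|---|---|---|
| On target | 0/28 = 0% | 1/28 = 3.6% |
| 3 days off | 5/28 = 17.9% | 7/28 = 25.0% |
| 7 days off | 13/28 = 46.4% | 15/28 = 53.6% |
| None in window | 100% | 100% |

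**3. Effect of the routine schedule.** The SAP does not give the interval between routine laboratory draws. If it is k weeks, a share 4/k of windows holds a routine draw. The chance that the reaction sample is used outright is then (4/k) × p + (1 − 4/k), where p is the middle column above.

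| Interval k | On target | 3 days off | 7 days off |
|---|---|---|---|
| 4 weeks | 0% | 17.9% | 46.4% |
| 8 weeks | 50% | 58.9% | 73.2% |
| 12 weeks | 66.7% | 72.6% | 82.1% |

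**4. Illustrative effect on a visit mean of CRP.** All inputs are assumptions: 80 subjects, 10% (8) with a reaction visit in the window, routine CRP 3 mg/L, reaction CRP 30 mg/L (a difference of 27), and routine draws spread evenly within ±3 days of target. A reaction sample is then nearer the target with probability 1.5/14 = 0.107.
- All subjects have a routine draw: 8 × 0.107 = 0.857 reaction values among 80. Mean = 3 + 27 × 0.857/80 = 3.3.
- Half do: 4 × 0.107 + 4 = 4.43 among 44. Mean = 3 + 27 × 4.43/44 = 5.7.
- A quarter do: 2 × 0.107 + 6 = 6.21 among 26. Mean = 3 + 27 × 6.21/26 = 9.5.
- None do: the mean is 30, from 8 subjects.

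**5. The same in SD units.** Bias = share of reaction values × their mean shift. Assumed shares of 2% to 20% and shifts of 0.5 to 2 SD give 0.02 × 0.5 = 0.01 SD up to 0.20 × 2 = 0.40 SD.

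**The case against.** The best defence is that Section 14.2 speaks of scheduled visits, Section 14.1 separates routine from reaction testing, and reaction visits have their own listing. One could read this as sending reaction samples to the listing and routine samples to the tables. It does not settle the matter. Table 1 defines each scheduled time point by its day window and applies to all assessments, the listing is not said to replace other uses, and the plotting sentence has no scheduled-visit limit. Nor need the choice await the protocol: SAP Section 3 gives the SAP's analysis methods precedence.

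Other points against do stand:

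- A reader might infer that reaction values will enter and will distort the long-term course. The text shows only that they can. The nearest-to-target rule keeps most of them out when routine draws are frequent and punctual.
- A reader might take the larger figures in the working, such as 5.7 mg/L (+91% over 3), as the expected effect. They rest on assumed routine coverage. A window with no routine draw at all is arguably not a scheduled laboratory visit, so it might not be displayed.
- A reader might picture mean CRP and complement curves. Section 14.2 says only that results are plotted. Means do appear in the by-visit statistics, but with the median, minimum and maximum (Section 4), so a few extreme values would show.
- No figure is available for C3 or C4, so neither the size nor the direction of their shift can be derived from the SAP.
- The first window opens on Day 8, so samples from Days 1 to 7 enter no window.
- The study is descriptive, and its primary objective, blood Phe, is unaffected. Extreme values remain visible in the shift tables, abnormality counts and listings.

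**Conclusion.** The defect lies in a rule the SAP states, not in a detail left out. Followed literally, Section 4.5 lets outcome-triggered CRP and C3/C4 replace, be averaged with, or stand in for routine values in the displays of Section 14.2. That can bias those displays toward reaction-time levels.

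The effect is small if routine draws are frequent and near target (CRP about 3.0 to 3.3 mg/L under the assumptions in the working) and larger where they are sparse. The true size cannot be stated without the laboratory schedule, the reaction rate and the analyte shift, none of which the SAP gives. The point concerns secondary, descriptive safety displays. It is worth correcting because the correction is cheap and hides no safety information.

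**What to change.** Add to Section 4.5, in words such as: *By-visit summaries and over-time plots of CRP, C3 and C4, and of any other laboratory analyte drawn because of a reaction, exclude samples from Hypersensitivity Reaction visits from window selection. These samples remain in the worst-post-baseline shift tables, the counts of CTC grade 3 or above and of out-of-range results, and the listings.*

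The exclusion should go no further. The SAP shows no event-triggered sampling of the routine antibody titres, and dropping all unscheduled draws would discard late or repeat samples that day-based windows are meant to capture.

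The cost is one sentence and a filter on visit type in the programming. The downside is small: some windows lose a value for some subjects.

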14.3 Vital Signs

Vital signs will include seated systolic blood pressure and diastolic blood pressure measured in millimeters of mercury (mm Hg), heart rate in beats per minute, respiration rate in breaths per minute, and temperature in degrees Celsius (°C).

Standard descriptive statistics will be presented for the observed and change from baseline values from parents studies (PAL-002, PAL-004, 165-205) at each visit. A subject listing will also be provided.

14.4 12-lead Electrocardiogram

The frequency of abnormalities and clinically significant abnormalities in 12-lead electrocardiogram will be summarized at each visit. A subject listing of ECG findings will be provided.

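### A clinically significant ECG can be left out of the only ECG summary table, because the window rule keeps one value, skips Days 1 to 7, and has no workable tie rule for ECG categories

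*SAP*

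**What the plan says.** **Scope.** SAP Section 4.5 does not limit its windows to efficacy or laboratory data: "Table 1 lists the visits assigned for the analyses of all assessments". It makes no exception for ECG. Table 2 is a second set of windows, for blood Phe only.

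**Selection.** Where a window holds two or more readings, "the assessment that is closest to the target day will be used for analyses". The result of the reading plays no part.

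**Ties.** For two equidistant readings the general rule is "then the average of the two assessments will be used for analyses". There is one exception: "If the measurement is a laboratory categorical variable, however, then the worse of the 2 equidistant measurements will be used".

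**Start of the grid.** The baseline row of Table 1 is pre-dose: "Last measurement prior to pegvaliase administration from parent studies (PAL-002, PAL-004, 165-205". The first post-baseline row is "Week 4 Day 22 Day 8 to Day 35". Under Section 4.4, Day 1 is the day of first pegvaliase dosing in the parent study.

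**ECG output.** Section 14.4 plans one summary, "The frequency of abnormalities and clinically significant abnormalities in 12-lead electrocardiogram will be summarized at each visit", and a subject listing of ECG findings. It plans no count of subjects with any abnormal ECG after baseline.

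**Laboratory output, for comparison.** Section 14.2 adds to its by-visit statistics the proportion of subjects with at least one result of grade 3 or above, the proportion with at least one result outside the normal range, and, for selected parameters, shift tables from baseline to the worst later value.

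**The concern.** A by-visit table that keeps one reading per window is a reasonable way to show a continuous variable over time. It is a weak way to show whether a subject ever had a clinically significant finding, because the reading that carries the finding may not be the one selected. For laboratory tests the SAP covers this with its any-time and worst-value displays. For ECG it does not, so the by-visit table has to do both jobs.

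Two further features make this worse. An ECG recorded in the first week after first exposure has no row to go to. And the tie rule, applied to a reading classed as normal or abnormal, gives an instruction that cannot be programmed.

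Safety and tolerability over long-term treatment are a secondary objective (Section 3.1). The printed windows run to Week 416, which at one every 4 weeks is 416 / 4 = 104 post-baseline visits. Even findings that are kept would be spread over many rows, and a reader could not add them up into a number of affected subjects.

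**Working it through.** **1. Rebuild Table 1.** For Week 4k the printed pattern is: target = 22 + 28(k − 1), window = Day 8 + 28(k − 1) to Day 35 + 28(k − 1).

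- k = 1: target 22, window 8 to 35. This matches the Week 4 row.
- k = 104: 28 × 103 = 2884, so target 2906, window 2892 to 2919. This matches the Week 416 row.

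All 14 printed rows reproduce. Each window is 28 days long, with 14 days before the target and 13 after it.

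**2. Days 1 to 7.** The lowest post-baseline day in any window is Day 8, and the baseline row takes pre-dose values only. A post-dose ECG on Days 1 to 7 therefore maps to no row. This follows from the text without further assumption.

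**3. From Day 8 on.** Assume one scheduled ECG and one unscheduled ECG on different days of the Week 4 window. Let d be the distance in days of the scheduled ECG from Day 22. The unscheduled ECG is dropped if it is further away than d. For d from 0 to 13 there are (14 − d) such days before the target and (13 − d) after it, so 27 − 2d of the 27 other days lose. For d = 14 none do. The scheduled day is not given in the SAP, so it is shown as a range:

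| Scheduled ECG on | d | Unscheduled dropped | Tied | Kept |
|---|---|---|---|---|
| Day 22 | 0 | 27/27 (100%) | 0 | 0 |
| Day 25 | 3 | 21/27 (78%) | 1 | 5 |
| Day 18 | 4 | 19/27 (70%) | 1 | 7 |
| Day 15 or 29 | 7 | 13/27 (48%) | 1 | 13 |
| Day 32 | 10 | 7/27 (26%) | 1 | 19 |
| Day 35 | 13 | 1/27 (4%) | 1 | 25 |
| Day 8 | 14 | 0/27 (0%) | 0 | 27 |

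If both days are uniform over the window, there are 28 × 27 = 756 ordered pairs. The unscheduled ECG is dropped in 27 + 2 × Σ(27 − 2d), d = 1 to 13, which is 27 + 2 × 169 = 365 pairs (48%). It is tied in 26 (3%) and kept in 365 (48%). If it is the only ECG in its window, it is always kept.

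**4. Ties.** ECGs on Day 18 and Day 26 are both 4 days from the target. If one is normal and the other abnormal, the general rule asks for their average. The worse-of-two exception does not apply, because an ECG category is not a laboratory variable. Two ECGs on the same day meet the same problem.

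**5. After the change.** A count over all on-treatment ECGs selects no single reading per window, so none is lost to steps 2 to 4.

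**The case against.** The strongest reply is that the harm depends on facts the SAP does not state.

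- **Reaction visits.** A reader might infer that ECGs prompted by reactions are systematically discarded. The SAP does not say that ECGs are done at reaction visits. Section 14.1 names IgE assays, CRP, C3/C4 and tryptase for those visits. The ECG schedule belongs to the protocol, which is not at hand. This objection stands, and the point is limited to off-target, unscheduled or early ECGs, whatever their cause.
- **Direction of bias.** A reader might also infer that the table is biased toward normal findings. The rule ignores the result. Bias would need unscheduled ECGs to be more often abnormal and a nearer ECG in the same window to be normal. Neither is documented, so no such claim is made.
- **Size.** A loss of 100% needs a scheduled ECG exactly on the target day. If routine ECGs are sparse, an unscheduled one is often alone in its window and is kept. This stands.
- **Other reporting.** The ECG listing carries no stated window restriction. The adverse event tables in Section 14 run from first dose to 30 days after last dose without visit windows, so a finding recorded as an adverse event is counted there. This stands: the finding leaves the ECG summary, not the report. But a listing gives no count of subjects, and this document does not settle which ECG findings become adverse events.
- **Days 1 to 7 are parent-study days, and the gap is not peculiar to ECG.** Both are true. But Section 4.2 presents the parent studies combined and all Phase 2 studies combined by default, so these days are within the reported data. Laboratory tests have any-time displays to cover the gap, and ECG has none.
- **Looser wording.** Section 14.4 refers to visits where Section 14.2 refers to scheduled visits, so unscheduled ECGs are not expressly barred. Section 4.5, however, covers all assessments, and the SAP defines no other set of visits for ECG.

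**Conclusion.** The point holds in a limited form. Under the stated rules a clinically significant ECG can be absent from the only ECG summary table. This is certain for a post-dose ECG on Days 1 to 7. From Day 8 it happens only when another ECG in the same window is nearer the target.

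In the two-ECG case the share of days on which this happens runs from 0% to 100% with the scheduled day, and is 48% if both days are uniform. Those figures assume exactly one scheduled and one unscheduled ECG on different days of the window. They are not an estimate of the loss in this study, which is unknown because the number and timing of unscheduled ECGs are not given.

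Separately, the tie rule cannot be applied to ECG categories. That is a defect of wording and does not depend on how many ties occur.

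The documents do not support saying that such findings vanish from the report, or that the primary objective is affected.

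**What to change.** 1. **Section 4.5.** Extend the worse-of-two tie rule from laboratory categorical variables to all categorical safety variables, and name ECG among them.
2. **Section 14.4.** Add a row to the ECG table: the number and percentage of subjects with any post-baseline abnormal ECG, and with any post-baseline clinically significant ECG, not present at baseline. Use every ECG within the safety data period of Section 14 (up to 30 days after last dose), including Days 1 to 7 and unscheduled ECGs. The by-visit frequencies can stay as they are.

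This brings to ECG the any-time approach that Section 14.2 already takes for laboratory tests. It needs a short change of wording in each section and one more table row, from data already collected. The abnormality counts may come out slightly higher than the by-visit table alone would suggest.
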